11.3 Analysis of Laboratory Data

Changes from Baseline in continuous laboratory parameters will be summarized by n, mean, standard deviation, minimum value, median, and maximum value for each treatment group. The mean change from Baseline will be compared between treatment groups at each time point using the ANOVA model with treatment as a factor. The differences between treatment groups and placebo for mean changes from Baseline will

be summarized using the mean, standard error, 95% confidence interval, and *P* value for the between-group difference.

Cross (Shift) tables from Baseline to the final value according to the normal range will be provided for each hematology, clinical chemistry parameter and urinalysis parameter except for the microscopic examination.

For selected laboratory parameter with Common Toxicity Criteria (CTC) a listing of all subjects with any laboratory determinations meeting CTC Version 4.03 (or later) of Grade ≥ 3 will be provided. For hemoglobin, an additional list will also be provided based on CTC Version 3.0 (or later) of Grade ≥ 2 . For each of these subjects, the whole course of the parameter will be listed. For subjects with laboratory values with CTC ≥ 3 , all of the laboratory parameters for those subjects will be listed.

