### **5.5.3            Method of Assigning Subjects to Treatment Groups**

All subjects will be centrally randomized using an Interactive Response Technology (IRT). Before the study is initiated, the telephone number and call-in directions for the IRT will be provided to each site.

All subjects will be assigned a unique identification number by the IRT at the Screening Visit. Subjects who meet the inclusion and none of the exclusion criteria defined in Section 5.2.1 and Section 5.2.2 will be centrally randomized 1:1:1:1:1:1 to one of six treatment groups at Baseline (Week 0) in a double-blind manner. The IRT will assign a randomization number that will encode the subject's treatment group assignment according to the randomization schedule generated by the Statistics Department at AbbVie.

IRT will provide the appropriate medication kit number(s) to dispense to each subject. Study drug will be administered at the study visits as summarized in Section 5.5. Returned study medication should not be re-dispensed to any subject.

At Week 16, all subjects will be re-randomized in a ratio of 1:1:1 to the three double-blind doses of ABT-494 (3 mg BID, 6 mg BID or 12 mg BID). The subjects who were re-randomized at Week 16 to ABT-494 24 mg QD prior to Protocol Amendment 2 will continue to receive the same double-blind dose until Week 52/PD.

The re-randomization will be stratified by the induction dose received during the first 16 weeks and by response status (responder versus non-responder) at Week 16. All subjects will keep the same unique subject identification number throughout the study.

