#### **8.1.7.3 Analysis of Laboratory and Vital Sign Data**

Changes from Baseline to minimum value, maximum value and final values in continuous laboratory and vital sign parameters will be summarized by treatment group. Treatment group differences between each of the ABT-494 dosing groups and the placebo group for mean changes from Baseline will be analyzed using ANOVA.

Vital signs and laboratory data will be described by statistical characteristics and frequency of abnormal values. Frequencies and percentages of subjects with laboratory shifts from Baseline to the final values using normal ranges to define categories (low, normal, high, and missing) will be summarized by the respective categories. Values beyond the normal values will be listed. Low or high laboratory values will also be flagged in the data listings.

Analysis details will be specified in the SAP.

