4.3 Sample Size

Approximately 210 subjects will be equally allocated to five treatment groups and the placebo group, representing a randomization ratio of 1:1:1:1:1. The sample size for this study is based on the expected proportion of subjects who achieve endoscopic remission at Week 12/16 and on the expected proportion of subjects who achieve clinical remission at Week 16. Assuming an endoscopic remission (as well as clinical remission) rate of 12% in the placebo arm and maximum of 35% in at least one of the ABT-494 BID treatment arms (3 mg BID, 6 mg BID, 12 mg BID and 24 mg BID) at Week 12/16, a sample size of 35 subjects per treatment group is sufficient to test for the presence of a dose response signal, to select the best dose response model for the observed data out of a prespecified set of candidate models, and to estimate target doses of interest (e.g., the minimum effective dose, MED) via modeling using MCP-Mod (Multiple comparison procedure and modeling) approach. This approach provides at least 80% average power to detect a dose effect at 5% level of significance (one-sided) with the linear, E_{max} , exponential, logistic, and sigEmax models pre-specified as likely candidates to characterize the dose-response for ABT-494 for the two co-primary endpoints of clinical and endoscopic remission.

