11.0 Safety Analysis

11.1 General Considerations

Adverse events (AEs), laboratory data and vital signs are the primary safety parameters in this study. All safety comparisons will be performed between treatment groups using the

safety analysis set. The safety variable will be summarized by treatment according to the treatment a subject actually received. The differences between treatment groups and placebo in safety parameters will be evaluated using two--sided tests at the significance level of 0.100.

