11.2 Analysis of Adverse Events

11.2.1 Treatment-Emergent Adverse Events

Treatment-emergent AEs for double-blind Induction period are defined as events that begin or worsen either on or after the first dose of the study medication and within 30 days after the last dose of the study medication for who subjects who discontinued study prior to double-blind Extension Period or up to the first dose of double-blind Extension Period for subjects who received at least a dose of study medication during double-blind extension period. An overview of treatment-emergent AEs, including AEs of special interest such as adverse events leading to death and adverse events leading to early termination, AEs by Medical Dictionary for Drug Regulatory Activities (MedDRA version 18.1 or later) preferred term and system organ class, AEs by maximum relationship to study drug, and AEs by maximum severity will be summarized by number and percentage. Treatment group differences (each ABT-494 dose group versus placebo group, as well as ABT-494 dose groups combined versus placebo group) in the overall incidence of treatment-emergent AEs will be assessed with Fisher's exact test for each preferred term for double-blind induction period.

Changes in laboratory data will be described using statistical characteristics and compared between treatment groups and placebo will be performed using a one-way Analysis of Variance (ANOVA). In addition, shift tables and listings will be provided for abnormal values, whereby the normal range of the analyzing laboratory will be used. Vital signs will be analyzed similarly.

The number and percent of subjects experiencing treatment-emergent adverse events will be summarized for the following adverse event categories. Comparisons of the percent of subjects experiencing an adverse event between treatment groups and placebo will be

performed using Fisher's exact tests. Only P values < 0.100 when rounded to three digits will be presented.

- Any treatment-emergent adverse event.
- Any treatment-emergent adverse event that was rated as possibly related to study drug by the investigator (Reasonable Possibility).
- Any treatment-emergent severe adverse event.
- Any treatment-emergent serious adverse event.
- Any treatment-emergent adverse event leading to discontinuation of study drug.
- Any treatment-emergent adverse event leading to death.
- Any treatment-emergent adverse event of special interest.

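### Induction laboratory and vital-sign changes are compared with placebo by treatment-only ANOVA; adding the baseline value already collected would tighten every such contrast at no cost in data

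*SAP*

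**What the plan says.** Induction SAP 11.3 gives the laboratory model: "The mean change from Baseline will be compared between treatment groups at each time point using the ANOVA model with treatment as a factor". Contrasts with placebo are then to "be summarized using the mean, standard error, 95% confidence interval, and *P* value for the between-group difference". Section 11.4 repeats the model and the same reported statistics for vital signs and weight, and section 11.2.1 describes the method as a one-way analysis of variance. The source is the protocol: in 8.1.7.3, differences between each dose group and placebo "for mean changes from Baseline will be analyzed using ANOVA", and 8.1.7 says the same in general terms.

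These are inferential comparisons. Induction SAP 11.1 lists laboratory data and vital signs among the primary safety parameters and tests differences from placebo two-sided at 0.100.

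No section gives a baseline-adjusted model for these data. Elsewhere the baseline value is used: Induction SAP 6.0 and 10.3 put it in the MMRM and ANCOVA for continuous efficacy variables, and protocol 8.1.9 puts it in the mixed model for pharmacodynamic biomarkers.

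**The concern.** A change score subtracts the whole baseline value, although follow-up predicts from baseline with slope rho when the variances are equal. If rho is below 1, the change score over-corrects and carries avoidable noise. ANCOVA estimates the slope and removes that noise.

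What is at stake is sensitivity to modest mean shifts with about 35 subjects per arm. Induction is the only placebo-controlled period; the Extension SAP (11.3, 11.4) summarizes laboratory and vital-sign changes without between-group tests. The protocol's introduction reports dose-related falls in red-cell mass in dogs, and its benefit-risk section reports changes in hemoglobin, lymphocytes, creatinine, lipids and transaminases with another JAK inhibitor. The documents give no reason for leaving the baseline value out of these models while using it for efficacy.

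**Working it through.** **A stated figure to reproduce.** There is none for these contrasts. The only power statement, at least 80% average MCP-Mod power, concerns the co-primary efficacy endpoints and does not bear on this point.

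**Inputs.**
- n = 35 per arm in six equal arms (Induction SAP 4.3; protocol 5.5.3).
- Two-sided 0.10 for safety tests (Induction SAP 11.1).
- rho is not in the documents, so 0.3 to 0.9 is an assumed range.
- Also assumed: equal variances at baseline and follow-up, a linear relation, and 35 evaluable subjects per arm.

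All quantities are in units of the parameter's SD.

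**Formulas for one dose-versus-placebo contrast.**
- Treatment-only ANOVA on change: variance = (2/n) × 2(1 − rho)
- ANCOVA with baseline: variance = (2/n) × (1 − rho²)
- Ratio ANOVA/ANCOVA = 2/(1 + rho); SE excess = √(2/(1 + rho)) − 1
- n per arm at which ANCOVA matches the planned ANOVA = 35 × (1 + rho)/2

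| rho | SE, ANOVA | SE, ANCOVA | SE excess | Matching n |
|---|---|---|---|---|
| 0.3 | 0.283 | 0.228 | 24.0% | 22.75 |
| 0.5 | 0.239 | 0.207 | 15.5% | 26.25 |
| 0.7 | 0.185 | 0.171 | 8.5% | 29.75 |
| 0.8 | 0.151 | 0.143 | 5.4% | 31.5 |
| 0.9 | 0.107 | 0.104 | 2.6% | 33.25 |

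Example at rho 0.5: √(2 × 1.0/35) = 0.239 and √(2 × 0.75/35) = 0.207.

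**Simulation check.** Six arms of 35 with 10,000 runs gave variance ratios of 1.333, 1.152 and 1.048 at rho 0.5, 0.7 and 0.9, against 1.333, 1.176 and 1.053 in theory. The mean error of both estimators was within 0.002 of zero.

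**Power.** For a true shift of 0.4 SD at two-sided 0.10, ANOVA against ANCOVA:
- rho 0.5: 51.1% against 61.3%
- rho 0.7: 69.7% against 75.7%
- rho 0.9: 98.2% against 98.6%

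**Chance imbalance.** A baseline difference D between two arms shifts the change-score contrast by −(1 − rho) × D. The SD of D is √(2/35) = 0.239, so a one-SD imbalance shifts the contrast, in the opposite direction, by 0.120, 0.072 or 0.024 SD at rho 0.5, 0.7 or 0.9. The simulated slopes were −0.50, −0.29 and −0.10, against about zero for ANCOVA. This is the same loss seen from another side:

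variance(ANOVA) = variance(ANCOVA) + (1 − rho)² × variance(D)

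At rho 0.5: 0.0429 + 0.25 × 0.0571 = 0.0571, whose square root is the 0.239 in the table.

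**Unequal variances.** With baseline and follow-up SDs sx and sy, the per-subject variance of change minus the ANCOVA residual variance is (sx − rho × sy)², which is never negative. The cost is one residual degree of freedom out of 210 − 6 = 204.

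**The case against.** The strongest defence is that nothing here is an error. One-way ANOVA on change is a standard, unbiased analysis, and the protocol and SAP agree on it. No decision rule in the documents turns on these P values: the stated dose-selection modelling is MCP-Mod on the co-primary efficacy endpoints (Induction SAP 10.1 and 10.2), individual laboratory findings are managed by thresholds (protocol 6.1.7), and an independent committee reviews unblinded safety data (protocol 6.1.9). For a parameter with rho near 0.9 the gain is negligible. The Extension SAP (3.0) also says the Induction SAP was signed off before the December 2016 lock.

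Most of this stands, and it rules out several stronger readings that a reader might infer:
- **That the planned contrasts are biased or their intervals invalid.** Randomization makes the estimator unbiased, and the noise from chance imbalance is already inside its standard error.
- **That imbalance is a second harm on top of the wider intervals.** The variance identity shows it is the same one.
- **That every safety comparison is affected.** Adverse events are compared by Fisher's exact test, shift tables and listings use no such model, and the Extension SAP tests nothing between groups for these data.
- **That dose selection is undermined.** No rule in the documents links these contrasts to it.

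None of this removes the precision gain. A passed lock limits how the change can now be made, but the plan as written still uses the less efficient model.

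**Conclusion.** The point holds as a free improvement to the Induction laboratory and vital-sign mean-change comparisons. The planned analysis is valid but less precise than it could be. Its standard error is larger than necessary by 2.6% to 24% over the assumed rho range of 0.9 to 0.3: material for parameters that vary a good deal within subjects, trivial for very stable ones. No primary or powered conclusion changes.

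The percentages rest on equal variances, a linear relation between baseline and follow-up, and an assumed rho. The SEs and power also assume 35 evaluable subjects per arm; missing data would make the SEs larger. The direction of the gain does not depend on equal variances. Its size for any given parameter cannot be settled from the documents.

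**What to change.** In Induction SAP 11.2.1, 11.3 and 11.4, and in protocol 8.1.7 and 8.1.7.3, replace the treatment-only ANOVA by ANCOVA on change from Baseline at each time point, with treatment as a factor and the baseline value of the same parameter as a covariate. Report the adjusted difference from placebo with its 95% confidence interval, and keep the unadjusted descriptive summaries as planned.

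Before lock, this costs one model term in the safety programs and the matching text changes, with no new data and no burden on subjects. If the Induction analysis is already locked, keep the planned ANOVA tables and add the adjusted contrasts as supplementary analyses, labelled as such.

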**Management of Select Laboratory Abnormalities:** For any given laboratory abnormality, the investigator should assess the subject, apply the standard of care for medical evaluation and treatment and follow any local guidelines. Laboratory abnormalities and changes in vital signs are considered to be adverse events only if they result in discontinuation from the study, necessitate therapeutic medical intervention, (meets protocol specific criteria [see Section [6.1.7](#) regarding toxicity management]) and/or if the investigator considers them to be adverse events. Specific toxicity management guidelines for abnormal laboratory values in hemoglobin, absolute neutrophil, absolute lymphocytes, total white blood cell, platelet, liver transaminases, and serum creatinine is described per the table below (confirmation by repeat testing is required).

---

Hemoglobin	

• If confirmed < 8.0 g/dL or decrease from BL > 2.0 g/dL, interrupt study drug dosing until hemoglobin value returns to normal reference range or its Baseline value.

Absolute neutrophil count (ANC)	

• If confirmed < 1000 cells/mm^3, interrupt study drug dosing until ANC value returns to normal reference range or its Baseline value.

• Discontinue study drug if confirmed < 500 cells/mm^3.

Absolute lymphocytes counts	

• If confirmed < 500 cells/mm^3, interrupt study drug dosing until absolute lymphocytes count returns to normal reference range or its Baseline value.

Total white blood cell count	

• If confirmed < 2000 cells/mm^3, interrupt study drug dosing until white blood cell count returns to normal reference range or its Baseline value.

Platelet count	

• If confirmed < 50,000 cells/mm^3 interrupt study drug dosing until platelet count returns to > 50,000 cells/mm^3 or its Baseline value.

AST or ALT	

• Discontinue study drug if confirmed ALT or AST > 3 × ULN with a Total Bilirubin > 2 × ULN or INR > 1.5.

• Discontinue study drug if confirmed ALT or AST > 8 × ULN.

• Discontinue study drug if confirmed ALT or AST > 5 × ULN for more than 2 weeks.

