11.3 Analysis of Laboratory Data

Changes from Induction Baseline during Extension in continuous laboratory parameters will be summarized by n, mean, standard deviation, and median value value for each treatment group.

Cross (Shift) tables from Induction Baseline to the final value according to the normal range will be provided for each hematology, clinical chemistry parameter and urinalysis parameter except for the microscopic examination.

For selected laboratory parameter with Common Toxicity Criteria (CTC) a listing of all subjects with any laboratory determinations meeting CTC Version 4.03 (or later) of Grade ≥ 3 will be provided. For hemoglobin, an additional list will also be provided based on CTC Version 3.0 (or later) of Grade ≥ 2 . For each of these subjects, the whole course of the parameter will be listed. For subjects with laboratory values with CTC ≥ 3 , all of the laboratory parameters for those subjects will be listed. For subjects with laboratory values with CTC 4, all of the laboratory parameters for those subjects will be listed.

For subjects who switched op open-label therapy, the above tables will also be presented by the open-label dose.

In addition, Cross (Shift) tables from Induction Baseline to the final value according to the normal range will be provided for each hematology, clinical chemistry parameter and urinalysis parameter except for the microscopic examination for the Any ABT-494 analysis set by quartile of average daily dose.

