11.3.1 Analysis of Liver Specific Laboratory Tests

The liver specific laboratory tests include the serum glutamic-pyruvic transaminase (ALT/SGPT), serum glutamic-oxaloacetic transaminase (AST/SGOT), alkaline phosphatase and total bilirubin. Each of these laboratory values will be categorized as follows:

1. $< 1.5 \times \text{ULN}$,
2. $\geq 1.5 \times \text{ULN} \text{ TO } < 3 \times \text{ULN}$,
3. $\geq 3 \times \text{ULN} \text{ TO } < 5 \times \text{ULN}$,
4. $\geq 5 \times \text{ULN} \text{ TO } < 8 \times \text{ULN}$, and
5. $\geq 8 \times \text{ULN}$,

where ULN is the upper normal limit.

Shift tables showing shift from Baseline to maximum and final values will be presented using these five categories.

A listing of potentially clinically significant liver function laboratory values will be provided. The listing will include all subjects who met any of the following 4 criteria:

1. ALT $\geq 2.5 \times$ ULN, or
2. AST $\geq 2.5 \times$ ULN, or
3. Alkaline Phosphatase $\geq 2.5 \times$ ULN, or
4. Total Bilirubin $\geq 1.5 \times$ ULN.

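### Both SAPs omit, without declaring it, the protocol's change-to-minimum/maximum laboratory summary; for non-hepatic tests the only categorical by-dose laboratory table left is a final-value shift that can miss toxicity that has resolved

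*SAP*

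**What the plan says.** Protocol 8.1.7.3 specifies two laboratory outputs. The first is continuous: "Changes from Baseline to minimum value, maximum value and final values in continuous laboratory and vital sign parameters will be summarized by treatment group". The second is categorical, and uses "laboratory shifts from Baseline to the final values using normal ranges to define categories".

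Induction SAP 11.3 keeps the categorical output: "Cross (Shift) tables from Baseline to the final value according to the normal range will be provided". Its continuous changes are "summarized by n, mean, standard deviation, minimum value, median, and maximum value for each treatment group", with group means compared at each time point. Extension SAP 11.3 also keeps the categorical output: "Cross (Shift) tables from Induction Baseline to the final value according to the normal range will be provided". Its cumulative shift tables by quartile of average daily dose likewise run to the final value. Its continuous changes are described by n, mean, SD and median only, and no time point is stated.

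Both SAPs also list subjects with any CTC Grade 3 or higher value (Grade 2 or higher for hemoglobin).

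Liver tests are treated differently. Induction SAP 11.3.1 adds a worst-value table: "Shift tables showing shift from Baseline to maximum and final values will be presented using these five categories". Extension SAP 11.3.1 counts subjects by as-treated group whose post-baseline values reach multiples of the upper limit of normal.

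Protocol 6.1.7 governs dosing when laboratory values cross thresholds. For hemoglobin the instruction is to "interrupt study drug dosing until hemoglobin value returns to normal reference range or its Baseline value". Neutrophils, lymphocytes, total white cells and creatinine have rules of the same form. The platelet rule has a different recovery level.

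**The concern.** The continuous summary that the protocol requires is the one that captures each subject's lowest and highest value. Without it, the remaining categorical by-dose table for hematology, creatinine and other non-hepatic tests looks only at the last value. The interruption rules are meant to hold dosing until the value recovers, so the subjects with the clearest toxicity are also those whose last value may look unremarkable.

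This is a dose-finding study, and laboratory toxicity by dose bears on dose choice. Protocol 3.0 reports red-cell, lymphocyte and renal tubular findings in animals. Protocol 3.2 reports hemoglobin, lymphocyte and creatinine effects with another JAK inhibitor. A by-dose count of affected subjects, taken from the laboratory data, is therefore worth having.

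**Working it through.** The plan gives no figure to reproduce, because no sample size, power or significance level is involved. The check is a comparison of sections, followed by a small count to show the mechanism.

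**1. Protocol against SAPs, non-hepatic laboratory parameters**

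| Output by treatment group | Protocol 8.1.7.3 | Induction SAP 11.3 | Extension SAP 11.3 |
|---|---|---|---|
| Change to subject's minimum | Yes | No | No |
| Change to subject's maximum | Yes | No | No |
| Normal-range shift to final value | Yes | Yes | Yes |
| Shift to worst value | No | No | No |
| Spread of change (min, max across subjects) | Not stated | Yes | No |

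The minimum and maximum in the Induction SAP's list are statistics of the distribution of change across subjects. They are not each subject's change to nadir or peak, so they do not supply the missing rows.

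**2. Is the omission declared?** Extension SAP 12.1 lists only efficacy variables as changes from the protocol. Induction SAP 12.1 has no entries.

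**3. Why the final value can miss a case.** Two triggers in Protocol 6.1.7 are relative to Baseline: a hemoglobin fall above 2.0 g/dL and a creatinine change above 1.5-fold. If the value is back at Baseline at the last measurement, the Baseline and final categories are the same and the subject is recorded as unshifted. Change to minimum or maximum measures the excursion directly.

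**4. Illustration (assumed data).** Take one arm of 35 with visits at Weeks 2, 4, 8, 12 and 16. Let k subjects each have one hemoglobin fall of 2.5 g/dL at Week 4, 8 or 12 and be back at Baseline by Week 16. All other changes are zero. Mean change to minimum = k × (−2.5)/35.

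| k | Falls above 2.0 g/dL at final value | Falls above 2.0 g/dL at subject's minimum | Mean change to minimum (g/dL) |
|---|---|---|---|
| 1 | 0/35 | 1/35 | −2.5/35 = −0.07 |
| 3 | 0/35 | 3/35 | −7.5/35 = −0.21 |
| 5 | 0/35 | 5/35 | −12.5/35 = −0.36 |

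The by-visit table behaves differently. At an affected visit with one or two cases, the mean is −0.07 or −0.14, the median is 0 and the minimum is −2.5. The Induction SAP reports that minimum, so the fall is visible there, although subjects are not counted across visits. The Extension SAP's mean, SD and median do not show it directly.

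**5. Do by-visit tables use every draw?** Both SAPs keep, within each window, the visit closest to schedule. In Extension SAP Table 2 the Week 20 to Week 44 windows are each 56 days wide (for example 57 − 2 + 1 = 56). A nadir at an unscheduled or repeat draw can therefore drop out.

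**The case against.** The case on the other side has real substance.

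- **The final-value shift is not a SAP departure.** Protocol 8.1.7.3 prescribes it and both SAPs implement it. A reader might infer that the SAPs weakened the shift table, but the documents do not support that. A worst-value shift table would be a new analysis, not a restored one.
- **Not all chemistry is affected.** ALT, AST, alkaline phosphatase and bilirubin have worst-value summaries in both SAPs.
- **Transient toxicity does not vanish from every by-dose table.** That stronger reading is tempting but wrong. Induction by-visit changes include the extremes. Adverse events are tabulated by treatment whether or not they recover. The events of special interest include anemia, neutropenia, renal dysfunction and CPK, with lymphopenia added in the Extension SAP. The CTC listings show the full course of the parameter.
- **Recovery is not guaranteed.** Protocol 6.1.7 holds dosing until recovery, but it does not ensure recovery before the last measurement. The platelet rule ends interruption once the count exceeds 50,000, which is below the entry limit of 100,000, so such a subject may still be low at the end. CPK and lipids have no interruption rule.
- **The SAP may set details.** Protocol 8.1.7.3 leaves analysis details to it.

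These points narrow the concern but do not remove it. Setting details does not cover silently leaving out a specified summary. The adverse event route depends on investigator reporting under a laboratory rule whose wording (Protocol 6.1.1.1 and 6.1.7) is ambiguous about whether meeting a toxicity criterion is enough by itself. The Induction table has no lymphopenia category, and neither SAP has one for platelets or total white cells. The CTC output is a listing, not a count by dose. Extension SAP 6.0 does say that shift summaries use all collected values, but that sentence belongs to a rule on same-day measurements, and section 11.3 still specifies the final value.

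**Conclusion.** The concern holds in a limited form. Both SAPs omit a by-treatment summary that the protocol requires, and neither says so. For non-hepatic parameters, the one remaining categorical by-dose laboratory table can miss hematology or creatinine toxicity that resolves after an interruption. The other outputs may show some of these cases, but none counts affected subjects by dose from the laboratory data. The gap is widest in the Extension SAP, whose continuous summary has no extremes.

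The size of the effect in this trial cannot be derived from the documents. The counts above show the mechanism under assumed transient falls with full recovery, and they say nothing about how often this occurs or how it varies with dose. The argument from interruption applies to hemoglobin, neutrophils, lymphocytes, white cells and creatinine, and only partly to platelets. For CPK it is simply that an earlier peak is not counted. No efficacy inference is affected.

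**What to change.** 1. In both SAPs, restore the protocol's summary: change from Baseline to each subject's minimum and maximum value, by dose, alongside the final value. The Extension SAP dates the Induction database lock to December 2016, so for that period these would be supplementary tables, labeled as such.
2. Add, and identify as a new analysis, shift tables by dose from Baseline to the worst on-treatment value for non-hepatic parameters: lowest for hemoglobin, neutrophils, lymphocytes, white cells and platelets; highest for creatinine and CPK. Use all on-treatment draws, including unscheduled and repeat ones.
3. Keep the final-value shift tables.
4. If the sponsor prefers not to restore the summary, record the omission and its reason in section 12.1 of each SAP.

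The cost is SAP wording and a few extra tables from data already collected. No clinical rule or visit schedule changes.
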